5.2 Participant Dispositions

The following summary outputs will be presented.

- **Reasons for screen failures** (as collected on the Study Termination Screen Failure CRF page) will be summarized using the ES.
- **Disposition of study participants screened** will be summarized using the ES for overall, by region and by site. In this summary, the site number, principal investigator name, first participant in date, last participant out date, will be captured by randomized treatment and by each analysis set (RS, SS, FAS).
- **Disposition of Analysis Sets** will be summarized by treatment group and overall for each analysis set (RS, SS) using the RS.
- **Disposition and Discontinuation Reasons** will be tabulated using the RS, and will contain the number and percentage of study participants by treatment group and overall who:
 - Started Treatment Period / SFU Period
 - Ongoing Treatment Period / SFU Period
 - Completed Treatment Period / Study
 - Discontinued Treatment Period / Study

Primary Reason for discontinuation (reason for treatment discontinuation as collected in the Study Medication Discontinuation CRF and primary reason for premature study termination as collected in the Study Termination Complete/Dropout CRF).

- **Discontinuation due to AEs** will be summarized by treatment group and overall for the following types of AEs using the RS:
 - AE, serious fatal,
 - AE, non-fatal,
 - Other (AE, non-serious fatal).

Listings of study participant disposition, study discontinuation and study participants who did not meet study eligibility criteria will be provided. The impact of COVID data will be listed.

5.3 Primary Endpoint Analysis

5.3.1 Definition of endpoint

Participants who reported no seizures for 28 consecutive days and maintained the seizure count as zero until the end of Treatment Period will be treated as meeting the primary endpoint.

For the purpose of deriving the primary efficacy endpoint, any intermittent missing diary

seizure count recording will not be imputed but considered as non-zero for the purposes of the primary endpoint.

A by-participant listing of daily seizure count will be provided, including seizure freedom, time to first occurrence of seizure freedom, time to seizure freedom, and duration of seizure freedom.

5.3.2 Main analytical approach

Participants meeting the primary endpoint will be defined using the strategies indicated below:

Estimand attributes:

1. Treatment conditions:

- Rozanolixizumab: Subcutaneous infusion, [REDACTED]
- Placebo: Subcutaneous infusion, 0.9% sodium chloride aqueous solution (physiological, saline, preservative free).

2. Population of interest: Study participants with LGI1 AIE who comply with the inclusion and exclusion criteria (Protocol Section 5.1 and Section 5.2).

3. Endpoint: Seizure freedom (defined by 28 consecutive days of no seizures) maintained until the end of the Treatment Period (Week 25).

4. Intercurrent events (ICE) / Intercurrent Event Strategy (ICES) and missing data strategies:

- ICE1: Temporary discontinuation from the IMP
- ICE2: Permanent discontinuation from the IMP

The strategies to handle ICEs are summarized below:

Table 5–2: Intercurrent events (ICE) / Intercurrent Event Strategy (ICES) and missing data strategies for the analysis of the primary endpoint

ICE	ICE Strategy	Missing Data Strategy
ICE1	Treatment Policy: The occurrence of intercurrent event ICE1 doesn't affect the assessment of primary endpoint. All seizure counts collected during the treatment period will be included in the assessment of primary endpoint.	See Section 5.1.3 for details.
ICE2	Composite strategy: Permanent discontinuation of the IMP will be considered as non achieving seizure freedom (non-responder).	

5. Population-level summary:

On the RS, odds ratio will be calculated to investigate the association between the treatment and chance to reach primary endpoint.

The ICEs will be handled per [Table 5–2](#).

The data will be summarized in 2×2 contingency table:

Table 5–3: 2 × 2 contingency table

	Rozanolixizumab	Placebo	Row Total
Seizure Freedom	A	B	A + B
No Seizure Freedom	C	D	C + D
Column Total	A + C	B + D	N

Note: A, B, C and D are the number of participants in the cells of the 2×2 table. N represents the total number of participants.

Hypothesis testing

Due to the low number of participants randomized to treatment there will be no hypothesis testing for the efficacy endpoints.

Treatment effect estimation

The OR estimate with its 95% CI will be reported in a summary table using the RS.

The estimate of OR will be computed as (see [Table 5–3](#))

$$\widehat{OR} = \frac{AD}{BC}$$

and reported to assess the strength and direction of the association with its 95% CI. Resulting $OR > 1$ indicates a clinical benefit from the RLZ, and the magnitude from 1 shows its strength.

In the case where none of the Placebo subjects reaches the primary endpoint, the calculation of the odds ratio estimate is not feasible as it requires division by zero ($B = 0$). In this situation, the OR is not estimable and the median unbiased estimator of the odds ratio (lower end of the 1-sided 50% CI) and 1-sided exact 95% CI will be reported.

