3 SAMPLE SIZE DETERMINATION

The study sample size of 60 participants is considered sufficient to provide acceptable study operating characteristics for the primary efficacy endpoint ([Section 1.1](#)). To account for an assumed 10% dropouts within each treatment arm and to enable an equal study participant allocation between treatment arms, 68 study participants will be randomly assigned to study treatment arms in a 1:1 ratio.

It should be noted that due to feasibility issues with recruitment, which was suspended as of 29 November 2023, the study has a limited sample size of 12 participants, which does not provide adequate statistical power to address the efficacy objectives defined for this study.

Given that there are limited randomized published studies in the LGI1 AIE patient population, there is uncertainty with respect to the expected proportion of participants who may achieve seizure freedom by 24 weeks in the control arm. While the targeted desirable treatment difference is 40%, a difference of 30% would be considered both clinically relevant and important in this disease area, given the lack of approved treatments and the length of prior corticosteroid treatment that is permissible in the study, along with potential prior disease specific treatment.

The study operating characteristics presented in [Table 3-1](#), were derived based on the expected seizure freedom proportions in the randomized study treatment arms that may be observed at the end of Treatment Period (Week 25). Based on Thompson et al (Thompson, 2018), after 30 and 90 days 51% and 88% of LGI1 AIE patients, respectively, experienced cessation of Faciobrachial Dystonic Seizures (FBDS) once treated with immunotherapy. These rates were consistent with (de Bruijn MAAM, 2019) median time to the FBDS freedom of 28 days once treated with immunotherapy.

For the purposes of the dual criteria framework as presented in [Table 3-1](#), the proportions of seizure freedom at the end of the Treatment Period (Week 25) are assumed not to be lower than 70% in the rozanolixizumab treatment arm and 40% in the placebo arm. The treatment effect evaluation based solely on statistical significance testing, is complemented with an assessment of its clinical relevance following the dual criteria framework as presented by (Fisch, 2015).

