Assuming 50% seizure-free proportions in the control arm, the sample size of 60 study participants will be able to detect a resulting 40% proportion difference with approximately 85% and a resulting 30% difference with approximately 55 to 65%. For a target difference (TD)

of 40% in the proportions between the treatment groups, the probability that both significance and relevance criteria are met, given a true difference of 40%, is at least 45% with only 9.5% of studies where none of the key criteria are met. If the TD achieved is 30%, the probability that both key criteria are met is at least 76%.

If the difference in proportions increases to 50%, because of a larger (90%) seizure-free proportion in the rozanolixizumab arm, the power to detect that effect is at least 95% with the sample size of 60. For this design, the probability that both the criteria are met is 79% and 44.5% for TD of 40% and 50%, respectively, with less than 1% probability that none of the criteria are fulfilled.

Decisions with respect to the outcome of this study will utilize the operating characteristics as described for the primary endpoint but will also importantly consider the strength of evidence of treatment effect provided by the secondary endpoints, according to the prescribed criteria for alpha spending, as outlined in protocol Section 9.3.2, as well as consideration to the safety data observed.

This document cannot be used to support any marketing authorization application and any extensions or variations thereof.
PUBLIC COPY

Table 3-1: Study Operating Characteristics

Sample size	PBO arm SF proportion (%) at the end of Treatment Period	RLZ arm SF proportion (%) at the end of Treatment Period	Power CMH ^a (%)	Power logistic ^b (%)	Target RLZ-PBO SF proportion difference (%)	Probability ^c (%)		
						Scenario A	Scenario B	Scenario C
60	40	70	54.6	63.2	30	45.7	20.6	33.8
					40	17.3	49.1	33.6
					50	3.7	62.8	33.5
60	40	80	84.5	86.0	30	76.3	14.1	9.6
					40	45.2	45.3	9.5
					50	16.1	74.7	9.2
60	40	90	98.3	95.4	30	95.6	3.8	0.6
					40	79.1	20.0	0.9
					50	44.5	54.8	0.7

CMH= Cochran-Mantel-Haenszel; PBO=placebo; RLZ=rozanolixizumab; SF=seizure freedom

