5.1.1.7 Multiple comparisons/multiplicity

A fallback hierarchical testing procedure was planned to be implemented to control the overall type I familywise error rate at 0.05 over the primary endpoint and the 4 defined secondary endpoints. See details in [Section Error! Reference source not found.](#). This however will no longer be implemented due to early study termination and the limited number of study participants.

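### After all efficacy testing was dropped at 12 participants, the SAP still says an odds ratio above 1 indicates clinical benefit and still ties decisions to 60-participant operating characteristics

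*SAP*

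**What the plan says.** SAP Amendment 1 withdraws inference consistently in several places. Section 3 records that recruitment stopped with 12 participants, "which does not provide adequate statistical power to address the efficacy objectives defined for this study". Section 2 says the primary endpoint will not be tested, Section 5.3.2 that "there will be no hypothesis testing for the efficacy endpoints", and Section 5.4 that the secondary endpoints will only be summarized. On the fallback multiplicity procedure, Section 5.1.1.7 says: "This however will no longer be implemented due to early study termination".

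Two other statements do not follow suit:

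- **Section 5.3.2, treatment effect estimation.** The OR is to be reported with its 95% CI. The text then says that a value above 1 "indicates a clinical benefit from the RLZ, and the magnitude from 1 shows its strength".
- **Section 3, last prose paragraph before Table 3-1.** "Decisions with respect to the outcome of this study will utilize the operating characteristics as described for the primary endpoint". The sentence goes on to bring in the strength of evidence from the secondary endpoints, judged by the alpha-spending criteria of protocol Section 9.3.2.

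Table 3-1 has rows for a sample size of 60 only.

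**The concern.** These statements bear on what the report may conclude about the primary endpoint.

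The 5.3.2 sentence links the direction of a point estimate to clinical benefit and its distance from 1 to strength, and asks nothing of the interval. With about six participants per arm, that distance is mostly noise.

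The Section 3 sentence points to decision properties that do not describe a 12-participant study, and to an alpha procedure that needs p-values the SAP no longer produces. It therefore cannot be carried out. Section 6.7, the place for changes to protocol-planned analyses, lists none, so nothing there overrides either sentence.

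**Working it through.** **Inputs from the documents.** Planned evaluable N is 60 (SAP Section 3: "The study sample size of 60 participants is considered sufficient to provide acceptable study operating characteristics for the primary efficacy endpoint"), with 1:1 allocation, so 30 per arm. Assumed seizure-freedom rates are 40% on placebo and 70%, 80% or 90% on rozanolixizumab. The dual criteria are confidence 0.975 that the difference exceeds zero and confidence 0.5 that it exceeds the target difference (TD). Actual N is 12.

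**Assumptions.** The documents give neither the arm split at 12 nor the prior behind the dual criteria. I take 6:6, with splits from 8:4 to 4:8 as the range, and uniform and Jeffreys beta priors.

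**1. Reproduce Table 3-1 at 30 per arm, 40% v 80%.**
- Power by the normal approximation with continuity correction: SE under the null = √(0.6×0.4×2/30) = 0.1265; SE under the alternative = √((0.24+0.16)/30) = 0.1155. Then z = (0.40 − 1/30 − 1.96×0.1265)/0.1155 = 1.03, giving 84.8%. The table says 84.5%.
- Dual criteria at TD 40: both met in 44.9% and neither in 9.1% to 9.5%. The table says 45.2% and 9.5%.

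So the table is right for 60 participants.

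**2. The direction rule with no true effect.** With equal arms, P(OR > 1) = (1 − P(equal counts))/2. For two Binomial(6, 0.4) counts, P(equal) = 0.231, so P(OR > 1) = 0.385. Unequal splits were enumerated exactly, with true rates from 20% to 80%:

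| Split of 12 | P(OR > 1), no effect |
|---|---|
| 6:6 | 36% to 39% |
| 7:5 or 5:7 | 46% to 52% |
| 8:4 or 4:8 | 38% to 43% |

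Tables with an infinite OR count as above 1. This includes tables with no placebo responder, where Section 5.3.2 calls the OR not estimable and substitutes a median unbiased estimate. Leaving those out at 6:6 gives 34.0% at a 40% rate and 16.1% at a 20% rate.

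At 30 per arm and 40%, the same probability is 44.8%. The weakness is in the rule, not the sample size.

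**3. Precision.** For 4/6 v 2/6, OR = (4×4)/(2×2) = 4.0 and SE(ln OR) = √(1/4+1/2+1/2+1/4) = 1.225. The Wald 95% CI is exp(1.386 ± 1.96×1.225) = 0.36 to 44. The same proportions at full size, 20/30 v 10/30, also give OR 4.0, with SE = √(1/20+1/10+1/10+1/20) = 0.548 and CI 1.4 to 11.7. The reading rule treats these two results alike.

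**4. Decision properties at 6 per arm, 40% v 80%, TD 40.**

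| | Both criteria met | Neither met |
|---|---|---|
| Table 3-1 (N=60) | 45.2% | 9.5% |
| N=12, uniform prior | 24.6% | 75.4% |
| N=12, Jeffreys prior | 32.2% | 51.0% |

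**5. Alpha spending.** Protocol Section 9.3.2 assigns 0.046, 0.002, 0.001 and 0.001 to the four secondary endpoints and compares p-values with these levels. The SAP plans no p-values, so the criterion has no input.

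**The case against.** The OR sentence can be read as an orientation note for the 2×2 table: which direction favours rozanolixizumab, and that distance from 1 measures association. The preceding words tie the OR to its 95% CI, and no success threshold is attached. This stands in part. It lowers the severity, but a direction note would speak of higher observed odds. The text says clinical benefit.

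The Section 3 paragraph repeats protocol Section 9.8 under a sample-size heading. The same section still states that "68 study participants will be randomly assigned to study treatment arms in a 1:1 ratio" before giving the 12-participant caveat, so it may simply preserve the original plan. No analysis in Section 5 computes the dual criteria or a go/no-go decision. This also stands in part: the paragraph is leftover text that nothing executes. It is still in the future tense and unlabelled, whereas Section 5.1.1.7 puts the same alpha procedure in the past tense and says it is dropped.

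A reader might infer that the report would end up claiming clinical benefit from chance. The documents do not support that: lack of power or absence of testing is stated in Sections 2, 3, 5.1.1.7, 5.3.2 and 5.4, and the interval appears beside the estimate. A reader might also blame the small sample for the 36% to 52% figure. The 44.8% at 30 per arm shows otherwise.

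**Conclusion.** Both statements are wrong as written, and the defect is minor to moderate. They conflict with the SAP's own withdrawal of testing, but no analysis, dataset or estimate depends on them.

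The direction rule says little when there is no effect, at any sample size. What the reduction to 12 changes is the width of the interval around a given OR and the chance of meeting both dual criteria, which falls from 45.2% to about 25% to 32% for 40% v 80% at TD 40. The N=12 results rest on an assumed split (6:6 for the dual criteria, 8:4 to 4:8 for the direction rule). The dual-criteria results also rest on an assumed uniform or Jeffreys prior, though both priors come close to the published table at 30 per arm.

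**What to change.** In Section 5.3.2, replace the sentence with: *OR > 1 means higher observed odds of seizure freedom on rozanolixizumab; the OR, its 95% CI and the responder counts are descriptive and do not by themselves support a conclusion of clinical benefit.*

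In Section 3, delete the last prose paragraph, on decisions, or mark it as the original plan, no longer applied at N=12.

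The cost is two text edits. No new analysis is needed and no planned output is lost. If the report is already written, the same descriptive wording belongs beside the OR there.

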5.4 Secondary Endpoints Analyses

All secondary efficacy endpoints will be summarized only and not tested for statistical significance due to the low number of participants recruited due to the study being terminated early.

5.4.1 Change in cognitive function (RBANS)

RBANS 5 domain index scores and total scale index score will be captured and calculated at the Screening visit, then post-Baseline visits 8, 16, 26, early treatment discontinuation visit and end of study visit according to the RBANS US v2.0 (13Nov2019) (see [Section 6.2](#)). The last available results of RBANS scores prior to first dose will be served as Baseline.

The observed Baseline and post-Baseline RBANS total scale index score at each scheduled visit where RBANS is collected will be summarized using descriptive statistics by randomized treatment group, together with the changes from Baseline. A by-participant listing of RBANS scores will be provided.

5.4.2 Change in overall disability: mRS

The mRS score will be captured according to the mRS manual (see [Section 6.3](#)).

The observed Baseline and post-Baseline mRS scores at each scheduled visit will be descriptively summarized on the RS by treatment group, together with the change from Baseline.

A by-participant listing of mRS category/score will be provided.

5.4.3 Use of rescue medication due to an absence or loss of clinical benefits

Use of rescue medications with associated reasons will be recorded as part of the assessment of prior and concomitant medications during the study. Participants with use of any rescue medications during Treatment Period due to an absence or loss of clinical benefit will be considered as meeting this endpoint.

A by-participant listing of use of rescue medication, PT of rescue medications and associated reasons will be provided.

5.4.4 Time to first occurrence of seizure freedom (TTFSF)

TTFSF will be summarized as a continuous variable by treatment group on the RS. A by-participant listing of time to first occurrence of seizure freedom will be provided.

5.5 Exploratory Endpoints Analyses

5.5.1 Seizure control

Seizure frequencies will be recorded on a daily basis across the 24 weeks of randomized therapy and during a variable Screening Period, based on the following categories:

1. 0 seizures
2. 1-5 seizures
3. 6-10 seizures
4. 11-20 seizures
5. >20 seizures

For each participant, a median category of seizure count categories will be calculated for each week that the participant is in the randomized treatment period, such that each participant has one average median category for that week, along with a minimum and maximum category range. In case of missing seizure count category, calculated median category will be rounded up to fit into the 5 categories. For example, if the calculated median is 2.5, then this value will be rounded up to 3 as the final median.

For the Screening Period, a Baseline median category will be calculated for each participant, in the same way as described for each week of randomized treatment. This will be to utilize the screening data collected in the period up to 6 weeks immediately prior to randomization.

The frequency counts and percentages of participants falling into each of the median categories across the 24 weeks will be summarized by treatment group using RS.

In the case of 7 missing data points over an entire week, this will be imputed from the previous weeks data. For 1 week of data, the median will not be calculated if more than 5 missing values.

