5.5.2 Duration of seizure-free period

The duration of the seizure-free period will be measured from the first day the participant reports no seizures of at least 28 consecutive days until the last day reported without seizures during the Treatment Period. Missing daily seizure counts will be treated as non-zero reports, without any value assigned. This statistic will be provided for each participant.

The endpoint will be included on the listing related to participants seizures; listed on the RS and by randomized treatment arm.

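### SAP 5.5.1 gives contradictory rules for a week with all 7 diary days missing, and on the workable reading a week with no data gets a seizure category while a week with one recorded day gets none

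*SAP*

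**What the plan says.** SAP 5.5.1 (Seizure control) reduces the daily diary to one median category per participant per week, on a five-level scale from 0 seizures to more than 20. Three sentences deal with missing days:

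- Partly missing weeks: "In case of missing seizure count category, calculated median category will be rounded up to fit into the 5 categories".
- Fully missing weeks: "In the case of 7 missing data points over an entire week, this will be imputed from the previous weeks data".
- Sparse weeks: "For 1 week of data, the median will not be calculated if more than 5 missing values".

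The weekly medians feed one table: "The frequency counts and percentages of participants falling into each of the median categories across the 24 weeks will be summarized by treatment group using" the Randomized Set. They also feed Baseline, where Screening weeks are handled like weeks on study medication: "For the Screening Period, a Baseline median category will be calculated for each participant, in the same way as described for each week of randomized" …

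Protocol 9.3.3.2 contains the rule for a fully missing week but has no limit at more than 5 missing days, so the clash arises from the sentence that the SAP adds. SAP 6.7, the list of changes to protocol-planned analyses, is marked as not applicable. SAP 6.1.7.1.1 (Efficacy data) does not settle the point. It applies an observed-case approach to named endpoints such as RBANS and mRS, and does not name seizure control.

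**The concern.** The two sentences on missing weeks stand next to each other and both cover a week with 7 missing days. One tells the programmer to fill it and the other says that no median is calculated. Two programmers could implement this differently, each with text to point to.

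The obvious way out is to let the specific rule override the general one. That gives an ordering that is hard to defend: no information yields a reported category, and one day of information yields nothing. The carry-forward also has no limit on consecutive filled weeks and no rule for a source week that has no value.

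At stake is how the weekly seizure-control table reads. The SAP no longer carries the good-control and moderate-control success criteria that the protocol planned to analyze, so this table is the main summary left for the endpoint.

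**Working it through.** The plan states no figure here to reproduce. The check applies the SAP 5.5.1 sentences to each possible number of missing days in a week, then sizes one filled week.

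**Step 1: the rules by number of missing days**

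| Days missing | Days observed | 7-missing sentence | More-than-5 sentence | Result |
|---|---|---|---|---|
| 0 to 5 | 7 to 2 | does not apply | median allowed | median of observed days, rounded up if needed |
| 6 | 1 | does not apply | no median | no value, no imputation given |
| 7 | 0 | use previous week | no median | contradictory; previous week's value if the specific rule governs |

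**Step 2: example weeks, with the specific rule governing.** Suppose every day of the previous week was category 1 (0 seizures).

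- Next week, 7 days missing: reported as category 1.
- Next week, 6 days missing and one day in category 5 (more than 20 seizures): no value, so the one recorded bad day does not reach the table.
- Next week, 5 days missing and the other two in categories 1 and 5: median (1 + 5)/2 = 3.
- A week with 6 missing followed by a week with 7 missing: the week to be copied has no value, and the text gives no other source.

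Two boundary cases are also open. The first Screening week has no previous week to copy. The text does not say whether treatment Week 1 may be filled from Screening.

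**Step 3: size of one filled participant-week**

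Inputs: 12 participants (SAP 3) and 1:1 randomization (SAP 1.2 and 3). The documents do not give the split by arm, so 6 per arm is an assumption. SAP 5.1 bases efficacy percentages on participants with observed data, shown as n/Nsub, unless otherwise specified. I assume that the other 5 in the arm are observed that week and that a filled week then joins the denominator.

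Let k of the 5 observed participants be in the category that receives the filled value.

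- Change in that category = (k + 1)/6 − k/5 = (5 − k)/30.
- k = 0: 5/30 = 16.7 points. k = 3: 2/30 = 6.7 points. k = 4: 1/30 = 3.3 points. k = 5: 0 points.
- A different category holding j of the 5 changes by j/6 − j/5 = −j/30, a fall of 0 to 16.7 points.

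The movement is therefore 0 to about 17 points. With k = 0 the change is 1/n for an arm of n, so arms of 7 and 5 would give maxima of 1/7 = 14.3 and 1/5 = 20 points. If fewer of the arm are observed that week, the maximum is also larger: with 4 observed before the fill it is 1/5 = 20 points.

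**The case against.** The strongest defence is that the sentences do different jobs: one imputes a week with no data, the other stops a median being calculated from too little. On that view the specific rule takes precedence and the result is workable, if uneven. That removes the literal contradiction, but it leaves the 6-versus-7 ordering and the missing source week untouched.

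A reader might go further and infer that the table systematically overstates seizure control, because people stop the diary when unwell and keep their last good week. The documents do not support that. Carry-forward copies whatever came before, so a bad week copied into a blank one understates control. Protocol 7.1.3 requires permanent discontinuation of study medication for clinical worsening as defined there, which leads to the early-discontinuation visit. Under SAP 5.1.1.2 that visit ends the Treatment Period, and weekly medians are calculated only within it. Protocol 5.1 requires a reliable caregiver, and under protocol 8.1.1 the caregiver may complete the diary and site staff review the printouts for completeness. Blank weeks remain possible, since entries lock after 72 hours, but nothing shows that they are frequent.

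A reader might also infer that the carry-forward breaks a uniform rule against crediting missing days as seizure-free. SAP 5.5.2 does say "Missing daily seizure counts will be treated as non-zero reports, without any value assigned", and SAP 5.3.1 also treats intermittent missing diary days as non-zero for the primary endpoint. But SAP Table 5-1 imputes missing daily counts for the primary endpoint with the period's average, so the SAP has no uniform rule to break. A weekly ordinal median is also a different quantity from a 28-day zero-seizure criterion.

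It also stands that a by-participant listing of daily seizure counts is planned (SAP 5.3.1), so the lone recorded day in a 6-missing week is not lost from the report.

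**Conclusion.** The point holds in a limited form. SAP 5.5.1 gives two instructions for a fully missing week, and the reading that rescues it values no data above one day of data and leaves the source undefined when the previous week is empty. This is a stated rule with an incoherent result, not merely absent detail.

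The consequence is minor: an exploratory table, descriptive only, in a study stopped at 12 participants with no efficacy testing. The primary endpoint is derived separately and is not affected. The range of 0 to about 17 points per filled participant-week is not a fixed effect of each fill. It rests on the assumptions in Step 3 of the working. The direction of any error depends on whether the copied week was better or worse than the unseen one.

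**What to change.** Replace the two sentences in SAP 5.5.1 with one rule. Suggested wording: *For any week with more than 5 missing diary days (6 or 7), no weekly median category is derived and no value is carried forward from another week. The number of participants without a weekly category is shown by week and treatment group.* Apply the same rule to the Screening weeks behind the Baseline category, which also settles the first-week cases.

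Treating 6 and 7 missing days alike by imputing both would also be coherent. Leaving both without a value is preferable because it follows the observed-data default in SAP 5.1 and needs no rule for an empty source week.

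The carry-forward is also in protocol 9.3.3.2, so its removal, and the limit at more than 5 missing days, should be entered in SAP 6.7. The cost is a short SAP edit, one entry in 6.7, an extra row in the table and a few more missing cells.
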